# Bioanalytical Measurements and Assay Methodology

Bioanalytical measurements of CRLX101 and camptothecin accumulation and pH dependent properties of CRLX101 and camptothecin (e.g. ratio of closed lactone form vs. open carboxylate from, release of camptothecin from CRLX101) will be conducted on an HPLC-FLD system using an assay developed and validated by the Clinical Pharmacology Program.

The urine sampling will also be used to monitor camptothecin exposure metrics specific to the bladder in order to correlate to toxicity and clinical response.

5.2.1 Plasma and Urine PK Sample Collection

All samples will be immediately placed on wet ice and refrigerated. The date and the exact time of each blood draw and urine samples should be recorded on the sample tube and the PK sheet provided.

5.2.2 Plasma Protein Measurement (VEGF)

VEGF protein expression has been shown to be reduced following the down-regulation of HIF-1 $\alpha$  in preclinical assessments *in vitro*. As a downstream target of HIF-1 $\alpha$  and a biomarker of angiogenesis, VEGF will serve as a surrogate biomarker for the efficacy of CRLX101. One 6 mL EDTA plasma tube (BD Franklin Lakes, NJ) will be collected from each participant prior to drug administration on C1D1 (baseline), C2D15, C6D1, and at disease progression to measure VEGF for anti-angiogenic activity.

The analyses will be performed with assays developed and validated in [name] laboratory using electrochemiluminescence technology that provides ultra-high sensitivity and very large signal dynamic range. The VEGF assay utilized by [name] laboratory has been used in previous studies evaluating anti-angiogenic therapies. (64) Purified protein standards will be used for generating standard curves for concentration determination.

Immediately after collection, invert the blood tube 8-10 times. Place the tube on wet ice and then store at 4°C in the refrigerator. The date and exact time of each blood draw should be recorded on the tube. Contact [name] lab for sample pick-up.

5.2.3 Circulating Tumor Cells (CTCs) and AR Analysis

Circulating tumor cells (CTCs), often prevalent in mCRPC, present a readily accessible 'liquid biopsy'. Methods to purify and analyze CTCs have been developed and widely utilized to help determine if biomarkers could be correlated with treatment response and/or disease progression. Of particular interest, the enumeration of CTCs and AR splice variant analyses have been shown to be potential clinical biomarkers of disease recurrence and treatment resistance.(65) The enumeration of CTCs with genomic instability has been shown to be a potential biomarker of treatment resistance and susceptibility to DNA damaging agents (e.g. camptothecin).(59, 60) Previously, the expression of  $\gamma$ -H2AX in biopsied tumor tissue has also been used to confirm the activity of CRLX101 (CRLX101 Investigator's Brochure); this study will assess this biomarker in CTCs if feasible.

Peripheral blood will be collected prior to treatment on C1D1 (baseline), C2D15, C6D1, and at disease progression. Two tubes of blood will be collected: one 10 mL Streck Cell-Free DNA (brown-black top) tubes and one 2.5 mL PAXgene tube.

# 5.2.4 EPIC Sciences

The blood collected in one Streck Cell-Free DNA tube will be shipped via FedEx Priority Overnight to Epic Sciences. These samples will be sent in ambient shippers provided by Epic Sciences to keep samples at room temperature. CTC detection and analysis (e.g. enumeration, AR expression, phenotypic genomic instability) will be assessed using the Epic Sciences platform technology. If feasible, detection of AR-V7 in CTCs may also be examined using the Epic AR-V7 test. Additionally, the expression of  $\gamma$ -H2AX in CTCs may be examined if feasible. Samples will be shipped to the following address:

Epic Sciences Attn: [name] [name] [contact]

Assuming this study treats at least 24 participants, at least 6 of these evaluable participants will have high phenotypic genomic instability CTCs at baseline as determined by the Epic Sciences algorithm. Differences in clinical response will be examined between participants who are positive for high phenotypic genomic instability CTCs in comparison to participants who are negative.

5.4 SAMPLE STORAGE, TRACKING AND DISPOSITION

All samples (except samples processed via the [name] Lab [NanoString] and EPIC Sciences [CTCs]) will be sent to and stored in [name].

Samples will be ordered in CRIS and tracked through Clinical Trial Data management system. Should a CRIS screen not be available, CRIS downtime procedures will be followed. Samples will not be sent outside NIH without appropriate approvals and/or agreements, if required. Any transfer of materials to other NIH or non-NIH investigators will occur following NIH Intramural Research Program guidelines. If the subject withdraws consent the participant's data will be excluded from future distributions, but data that have already been distributed for approved research use will not be able to be retrieved.

# 5.4.1 Clinical Pharmacology Program ([name] Lab)

Upon arrival in the Clinical Pharmacology Program, blood samples will be centrifuged and the plasma transferred into cryovials for storage at -80° C until the time of analysis. Urine samples will be aliquoted into cryovials, diluted with an equal volume of methanol and stored at -80°C until the time of analysis. In addition, samples will be barcoded.

All samples sent to the Blood Processing Core (BPC) will be barcoded, with data entered and stored in the Labmatrix utilized by the BPC. This is a secure program, with access to Labmatrix limited to defined [name] lab personnel, who are issued individual user accounts. Installation of Labmatrix is limited to computers specified by [name]. These computers all have a password restricted login screen.

Labmatrix creates a unique barcode ID for every sample and sample box, which cannot be traced back to participants without Labmatrix access. The data recorded for each sample includes the participant ID, name, trial name/protocol number, time drawn, cycle time point, dose, material type, as well as box and freezer location. Participant demographics associated with the clinical center participant number are provided in the system. For each sample, there are notes associated with the processing method (delay in sample processing, storage conditions on the ward, etc.).

Barcoded samples are stored in bar-coded boxes in locked freezers at either -20 C or -80 C according to stability requirements. These freezers are located onsite in the CPP and offsite at NCI Frederick Central Repository Services in Frederick, MD. Samples will be stored until requested by a researcher named on the protocol.

All requests are monitored and tracked in Labmatrix. All researchers are required to sign a form stating that the samples are only to be used for research purposes associated with this trial (as per IRB approved protocol) and that any unused samples must be returned to the CPP. It is the responsibility of the NCI Principal Investigator to ensure that the samples requested are being used in a manner consistent with IRB approval.

Following completion of this study, samples will remain in storage as detailed above. Access to these samples will only be granted following IRB approval of an additional protocol, granting the rights to use the material. If, at any time, a participant withdraws from the study and does not wish for their existing samples to be utilized, the individual must provide a written request. Following receipt of this request, the samples will be destroyed (or returned to the participant, if

so requested). The PI will record any loss or unanticipated destruction of samples as a deviation. Reporting will be per the requirements of section 7.2.

Sample barcodes are linked to participant demographics and limited clinical information. This information will only be provided to investigators listed on this protocol, via registered use of the Labmatrix. It is critical that the sample remains linked to participant information such as race, age, dates of diagnosis and death, and histological information about the tumor, in order to correlate genotype with these variables.

# 5.4.2 Molecular Targets Core ([name])

Biospecimens will be collected and processed using validated SOPs that will ensure both specimen quality and participant confidentiality pursuant to informed consent provisions. To ensure participant confidentiality, only containers used for the initial specimen collections will be labeled with participant identifiers. Coded, linked labels will be applied to all subsequent specimen containers. When specimens are processed and aliquoted, no participant information will be included on the new containers. Samples are labeled with printed consecutive numbers, frozen on dry ice, and stored in a -80°C freezer located at the NCI Research Facility. The freezer is locked and monitored 24/7 for temperature control. Samples will be tracked using a limited access Excel database.

Access to the inventory system and associated documents will be restricted to appropriate personnel only. Requests to use specimens stored in the repository must be approved by the IRB. SOPs ensure that any changes in the informed consent made by a participant and relayed to the PI will be reflected in the inventory system to ensure that specimens are destroyed as appropriate. All laboratory personnel will be trained to adhere to SOPs and will be monitored for high-quality performance. The PI will record any loss or unanticipated destruction of samples as a deviation. Reporting will be per the requirements of section **7.2**.

# 5.4.3 [name] Lab

Tracking and disposition of samples will conform to the NCI CCR Biospecimen Guidelines.

All samples will be barcoded and data entered and stored in the Labmatrix system utilized by the NIH Clinical Center. This is a secure system with access limited to defined personnel.

Labmatrix creates a unique barcode ID for every sample which cannot be traced back to subjects without Labmatrix access. The data recorded for each sample includes the subject ID, name, trial name/protocol number, date/time drawn, as well as box and freezer location. Subject demographics associated with the clinical center participant number are provided in the system. For each sample, there are notes associated with the processing method (delay in sample processing, storage conditions on the ward, etc.). Access to personally identifiable information (PII) is limited to the PI and associate investigators.

An additional layer of encryption will be added for samples undergoing genetic analysis in the [name] lab where a separate clinically annotated unique sample ID will be generated linked with the sample ID in Labmatrix. As additional clinical information is generated and linked to the unique participant ID, it is also electronically linked via Labmatrix to the sample ID. The [name] lab will proceed with sample analysis and record data under the unique sample ID.

Barcoded samples are stored in barcoded boxes in a locked freezer at either -20 or -80°C or in liquid nitrogen according to stability requirements. These freezers are located onsite, and access to stored clinical samples is restricted. Samples will be stored until requested by a researcher named on the protocol. All requests are monitored and tracked in the Labmatrix System. All researchers are required to sign a form stating that the samples are only to be used for research purposes associated with this trial (as per the IRB approved protocol) and that any unused samples must be returned to the NCI. It is the responsibility of the NCI Principal Investigator to ensure that the samples requested are being used in a manner consistent with IRB approval.

Samples will be stored in a freezer at either -4°C or -70°C behind a door locked after working hours. Samples will be tracked by a designated member of the laboratory who is responsible for notifying the PI about requests for use of the material, for allocating the material to other members of the laboratory, for recording the disposition of the allocated material.

# 5.4.4 Future Use/IRB Reporting/Protocol Completion/Sample Destruction

Blood and tissue specimens collected in the course of this research project may be banked and used in the future to investigate new scientific questions related to this study, including gene/protein expression and germline analysis. However, this research may only be done if the risks of the new questions were covered in the consent document and the proposed research has undergone prospective IRB review and approval.

The PI will record any loss or unanticipated destruction of samples as a deviation. Reporting will be per the requirements of section 7.2. If the subject withdraws consent the participants data will be excluded from future distributions, but data that have already been distributed for approved research use will not be able to be retrieved.

# **6 DATA COLLECTION AND EVALUATION**

# 6.1 DATA COLLECTION

The PI will be responsible for overseeing entry of data into an in-house password protected electronic system, C3D, and ensuring data accuracy, consistency and timeliness. The principal investigator, associate investigators/research nurses and/or contracted data manager will assist with the data management efforts. All data obtained during the conduct of the protocol will be kept in secure network drives or in approved alternative sites that comply with NIH security standards. Primary and final analyzed data will have identifiers so that research data can be attributed to an individual human subject participant.

All adverse events, including clinically significant abnormal findings on laboratory evaluations, regardless of severity, will be followed until return to baseline or stabilization of event.

Document AEs from the first study intervention, Study Day 1, through 30 days after the last dose of study therapy. Beyond 30 days after the last of study therapy, only adverse events which are serious and related to the study intervention need to be recorded.

An abnormal laboratory value will be recorded in the database as an AE **only** if the laboratory abnormality is characterized by any of the following:

- Results in discontinuation from the study
- Is associated with clinical signs or symptoms

- Requires treatment or any other therapeutic intervention
- Is associated with death or another serious adverse event, including hospitalization.
- Is judged by the Investigator to be of significant clinical impact
- If any abnormal laboratory result is considered clinically significant, the investigator will provide details about the action taken with respect to the test drug and about the participant's outcome.

As the toxicity profile of Enzalutamide and CRLX101 is well defined and published, expected grade 1 clinical adverse events will not be recorded in the database.

**End of study procedures:** Data will be stored according to HHS, FDA regulations and NIH Intramural Records Retention Schedule as applicable.

**Loss or destruction of data:** Should we become aware that a major breach in our plan to protect subject confidentiality and trial data has occurred, this will be reported expeditiously per requirements in section **7.2.1**.

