### 1.2.5.9 Camptothecin-Induced Cystitis

Cystitis is a common adverse event following CRLX101 administration. The proposed mechanism of toxicity involves the reclosing of the camptothecin lactone ring once the drug is cleared into the more acidic pH of the bladder. The closed lactone ring leads to reactivation of camptothecin, thus increasing the likelihood for off-target effect and subsequent toxicity in the bladder. The current management of the risk for cystitis involves dilution of the urine via increased hydration. Alkalinization of the urine is another proposed method of prophylaxis, which could be achieved via sodium bicarbonate administration. Although higher urine pH will limit the concentration of active camptothecin, it could lead to higher release of CPT from intact CRLX101 nanoparticles that are cleared renally. The use of sodium bicarbonate to circumvent high grade camptothecin-induced cystitis requires further investigation.

*In vitro* experiments were conducted at varying pH levels in urine following a 72-hour incubation at 37°C to measure the release of CPT from the CRLX101 nanoparticle and the ratio of lactone to carboxylate of the unconjugated CPT. While increasing pH lead to an increased rate of CPT release, the ratio of CPT species favored the carboxylate form, especially at pH values of 8 or greater (See Figure 5). Despite a higher concentration of total CPT, urine alkalinization led to a decrease in the active lactone form compared to lower urine pH values.

[figure not shown]

Figure 5: Total concentration of free CPT released from CRLX101 at various pH values (left) and the percentage of carboxylate form graphed against percentage of lactone form at various pH values (right).

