# 8.3 REPORTING OF SERIOUS ADVERSE EVENTS

Any AE that meets protocol-defined serious criteria, or meets the definition of Adverse Event of Special Interest that require expedited reporting must be submitted immediately (within 24 hours of awareness) to OSRO Safety using the CCR SAE report form.

All SAE reporting must include the elements described in 8.2.

SAE reports will be submitted to the Center for Cancer Research (CCR) at: [contact] and to the CCR PI and study coordinator. CCR SAE report form and instructions can be found at:

https://ccrod.cancer.gov/confluence/pages/viewpage.action?pageId=157942842

Following the assessment of the SAE by OSRO, other supporting documentation of the event may be requested by the OSRO Safety and should be provided as soon as possible.

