8.4.2 To Be Reported by the Research team

8.4.2.1 Adverse Events of Special Interest (AESI) associated with CRLX101

For all subjects, the following adverse events are categorized as Adverse Events of Special Interest (AESI) associated with CRLX101:

- Infusion-related hypersensitivity reaction(s) of any grade
- Any newly developed cystitis (including Grade 1) in subjects without cystitis at baseline

Any occurrence of hypersensitivity/allergic reactions and/or cystitis a patient experiences associated with CRLX101 must be reported to Ellipses Pharma within 1-2 business days of learning of its occurrence using the OSRO Serious Adverse Event Form.

AESIs will be sent to Ellipses Pharma via their safety vendor, Simbec-Orion by email to: [contact]

Or alternatively by fax to: [contact] or back-up [contact] .

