## 10.4.4 Safety Analyses

Safety of the agent will be assessed by determining the grade of adverse events noted in each participant, and reporting the fraction with grade 3 and grade 4 adverse events. Participants who receive at least one dose of the study treatments will be evaluable for safety. Safety data will be presented in a summary. Results from the safety evaluation in the initial 3-6 participant safety cohort will be reported separately from safety data from participants included in the efficacy cohort. The safety data will consist of the reporting of all adverse events, and may also include reporting vital signs, physical examination data, and laboratory safety data.

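### The rule that keeps expected grade 1 adverse events out of the database makes no exception for the events of special interest, so any-grade cystitis and infusion-reaction counts taken from it would be too low

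*Combined protocol and SAP*

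**What the plan says.** The recording rule is in Section 6.1: "expected grade 1 clinical adverse events" are not entered in the database, on the ground that the toxicity of both drugs is already well described. No exception follows, and the word expected is not defined there.

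Section 8.4.2.1 lists two events of special interest for CRLX101: infusion-related hypersensitivity of any grade, and "Any newly developed cystitis (including Grade 1) in subjects without cystitis at baseline". Both are reported to the collaborator within 1-2 business days, "using the OSRO Serious Adverse Event Form". Section 8.3 adds a sponsor route: an event that "meets the definition of Adverse Event of Special Interest that require expedited reporting must be submitted immediately" goes to the sponsor's safety office within 24 hours.

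On analysis, Section 10.4.4 says: "The safety data will consist of the reporting of all adverse events". Exploratory objective 1.1.3.2 concerns the mechanism of camptothecin-induced cystitis. The urine assay text under Section 5.1.1.2 plans to monitor camptothecin "exposure metrics specific to the bladder in order to correlate to toxicity and clinical response".

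**The concern.** The same event falls under two instructions. A new grade 1 cystitis must be reported on a safety form within days, yet as an expected grade 1 event it is kept out of the dataset from which safety tables would ordinarily be built. A table of cystitis or infusion reactions at any grade would then count only grade 2 and above, without saying so, under a section that promises all adverse events. The trial singles these two toxicities out for special reporting, and it uses C2D15 to study urine alkalinization as a possible way to prevent cystitis.

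**Working it through.** The plan states no figure that depends on this rule, so the main check is textual. The arithmetic only gives the scale.

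**Step 1. Are the events expected?** Section 1.2.5.9 says: "Cystitis is a common adverse event following CRLX101 administration". Section 1.2.5 lists both cystitis and infusion-related reaction among the toxicities commonly reported with CRLX101. Any ordinary reading of expected covers both, so their grade 1 events fall under the Section 6.1 exclusion.

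**Step 2. Does another instruction bring them into the database?** Section 8.2 requires serious adverse events to be captured in the clinical database. Nothing equivalent covers a non-serious event of special interest. Sections 8.3 and 8.4.2.1 send forms to the sponsor's safety office and the collaborator. No section reconciles those forms with the database.

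**Step 3. Can Section 10.4.4 be met?** Not from the database alone: for expected grade 1 events, Section 6.1 removes what Section 10.4.4 promises.

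**Step 4. How many cystitis cases might there be?** Expected cases = participants × any-grade rate. Section 10.2 gives the participant numbers. The maximum evaluable is 6 + 21 = 27. If the trial stops after stage one, it is 3 + 8 = 11 to 6 + 8 = 14. At a 25% success rate the chance of that stop is P(X ≤ 2), X ~ Bin(8, 0.25), = 0.6785, which agrees with the plan's 67.9%.

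| Source (protocol section) | Any-grade cystitis | n = 11 | n = 14 | n = 27 |
|---|---|---|---|---|
| CRLX-002 (1.2.5.7.1) | 8/97 = 8.2% | 0.9 | 1.2 | 2.2 |
| CRLX101-208, with bevacizumab (1.2.5.7.2) | 7/55 = 12.7% | 1.4 | 1.8 | 3.4 |
| CRLX-001, at the MTD (1.2.5.7.1) | 11/44 = 25% | 2.8 | 3.5 | 6.8 |
| CRLX-001, all dose levels (1.2.5.7.1) | 27% | 3.0 | 3.8 | 7.3 |

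That is about 2 to 7 cases at 27 participants and about 1 to 4 after a stage-one stop. At 27 participants, even the lowest rate gives a chance of at least one case of 1 − (1 − 8/97)^27 = 0.90.

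**Step 5. How many of those would be grade 1?** The documents do not say. They do bound the high grades in two studies. In CRLX-002, neutropenia is the only grade 3 or higher event reported in more than one patient, so at most 1 of the 8 cystitis cases reached grade 3. In CRLX101-208, cystitis is absent from the corresponding list, so at most 1 of 7 did. At least 13 of these 15 cases were therefore grade 1 or 2, with the split between the two unknown. If 25% to 75% of cases peak at grade 1 (an assumption), the number missing from the database would be 0.25 × 2.2 = 0.6 to 0.75 × 7.3 = 5.5 at 27 participants, and 0.25 × 0.9 = 0.2 to 0.75 × 3.8 = 2.8 after a stage-one stop.

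No comparable figure can be given for infusion reactions. Section 1.2.5.8 says only that they occurred in a small number of subjects.

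**The case against.** The strongest reply is that the sponsor already holds these events. The research team files the special-interest form, and Section 8.3 brings those needing expedited reporting to the sponsor's own safety office. Section 8.4.2.1 also asks for any occurrence of cystitis or hypersensitivity associated with CRLX101. Section 6.1 itself has all adverse events followed regardless of severity. This stands: a reader might infer that grade 1 cystitis is lost to the trial, and the documents do not support that. What is missing is its place in the database and any step that brings the forms back to it.

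A reader might also infer that the cystitis objective is undermined, or that the exposure-toxicity analysis will be biased toward no relation. The documents do not support either. The objective rests mainly on comparing urine camptothecin species between C1D1 and C2D15, which the recording rule does not touch. The correlation with toxicity is one general sentence, with no stated data source or coding of cystitis. Grade 1 cases would count as unaffected only if the analysis takes cystitis from the database.

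Two further points stand. The word expected is undefined, so classing cystitis under it is an inference, though a well-supported one. And the only safety summary specified by grade is the fraction with grade 3 and grade 4 events, which the rule leaves intact. Neither removes the conflict between Sections 6.1, 8.4.2.1 and 10.4.4.

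**Conclusion.** The conflict is real and should be corrected, but its reach is limited. Followed exactly, Section 6.1 makes any-grade counts of cystitis and infusion reactions from the study database too low, and Section 10.4.4 cannot deliver all adverse events from that source. The exploratory link between bladder exposure and toxicity could miss grade 1 cases if it uses the database. Dose-limiting toxicities, grade 3 and 4 fractions, the urine camptothecin comparison and the two-stage efficacy decision are unaffected.

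For scale, about 2 to 7 cystitis cases of any grade are expected at 27 participants, or about 1 to 4 after a stage-one stop. This assumes that the earlier CRLX101 rates carry over to the combination with enzalutamide. A reader might settle on about 7 cases, but that takes the highest documented rate, pooled over all CRLX-001 dose levels, at the maximum sample size. How many would be grade 1 cannot be established from the documents.

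**What to change.** In Section 6.1, keep the exclusion and add: *except the adverse events of special interest in Section 8.4.2.1 (infusion-related hypersensitivity and cystitis), which are recorded in the database at every grade.* In Section 10.4.4, state that other expected grade 1 events are not included in the safety data.

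The cost is two sentences and a few extra database entries for events already reported on a form. Extending the exception to dysuria or hematuria would be new collection, because neither is on the special-interest list, and it is not needed to resolve the conflict.
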